The results of our recent LMA trial indicate that surfactant delivery via LMA produces immediate improvements in oxygenation comparable to delivery via ETT, and decreased need for subsequent ventilatory support. However, because our previous INSURE approach for ETT delivery of surfactant included morphine, a slow-onset, long acting analgesic which likely contributed to the need for invasive ventilation, it remains unclear whether LMA delivery of surfactant is as effective as our new INSURE technique, which is designed to avoid respiratory depression.

Since our last trial began, the results of a small randomized trial were published, where the 11 babies who received surfactant via LMA showed improvements in oxygenation comparable to those in our study, whereas no change occurred in the surfactant-untreated (CPAP-only) group (Attridge, Stewart, Stukenborg, & Kattwinkel, 2013). In a piglet model of RDS, surfactant administered via LMA had physiologic effects similar to those of ETT administration (Roberts et al., 2010). The only ongoing clinical trial on delivery of surfactant via LMA to human neonates with RDS (Roberts et al., NCT01116921 at www.clinicaltrials.gov) is examining the effectiveness of this procedure (versus no surfactant treatment) in decreasing the need for later mechanical ventilation.

From the foregoing, it is apparent that clinical trials are still needed to address the relative efficacy of surfactant delivered via LMA versus optimized INSURE approaches. In this proposal, we extend our investigations of surfactant delivery by LMA to the current clinical context in which premedication for INSURE comprises atropine and remifentanil.

Hypothesis:

Surfactant therapy delivered via LMA is not inferior to surfactant therapy delivered via transient intubation (INSURE technique) with short-acting narcotic premedication for mild to moderate RDS in preterm neonates.

Aims:

1. To compare the rate of failure of surfactant therapy delivered via LMA to the rate of failure of surfactant therapy delivered via transient intubation (INSURE technique) in avoiding mechanical ventilation in neonates 27 to 36 weeks' gestation with mild to moderate RDS.

1a. To evaluate the success of remifentanil as premedication for transient intubation (INSURE technique) as compared to morphine used in our previous trial.

2. To further evaluate the safety of surfactant administration via LMA.

B. Study Design/C. Subject Population

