- Multi-center, randomized controlled trial. The participating centers are Albany Medical Center, Bellevue Woman's Center at Ellis Hospital, and Golisano Children's Hospital. Each center will obtain approval from that center's own Institutional Review Board. It is anticipated that the study will take 2 years to complete.

[figure not shown]
Patient Enrollment:

- The investigators and/or study coordinator will evaluate all infants admitted to the NICU who are less than 48 hours of life from 27 through 36 completed weeks' gestation with mild-moderate RDS.
- If they meet the pre-defined inclusion criteria and informed consent is obtained, they will be randomized to either the INSURE group or LMA group for the initial surfactant administration. Patients will be block randomized in one of three gestational age groups: 27 0/7 - 28 6/7 weeks, 29 0/7 - 32 6/7 weeks, 33 0/7 - 36 6/7 weeks.
- Randomization process: An anticipated 130 patients will be enrolled in the study. Patients will be randomized into three groups using a blind randomization selection method. After computer-generated block randomization, the 130 numbered cards will be placed in sealed, numbered envelopes, and kept in a NICU nurse practitioner office. Each card will indicate LMA or INSURE group and include an identifier code number. After obtaining the signed consent form, the investigators or coordinator will open the next envelope in the appropriate gestational age block.
- Inclusion Criteria:
 - Gestational age (GA) 27 0/7 weeks to 36 6/7 weeks
 - Age < 48 hours
 - Mild-moderate RDS as defined by an FiO₂ requirement of 0.30 - 0.60 on either CPAP or nasal intermittent positive pressure ventilation (NIPPV) for at least two hours to maintain SpO₂ 90-95%
 - Written consent obtained
- Exclusion Criteria:
 - Prior tracheal intubation

- Prior surfactant therapy
- Evidence of pneumothorax, pneumomediastinum, or pneumopericardium
- $\text{FiO}_2 > 0.60$
- Craniofacial or other airway malformation
- Major congenital malformation (cardiac and thoracic defects)
- Apgar score of ≤ 3 at 5 minutes of life or evidence of encephalopathy
- Weight less than 800 grams

Study/Intervention:

The diagram below is a graphic depiction of the study protocol. Criteria for assisted ventilation and other respiratory support will be the same for both groups.

• **INSURE (control group): Atropine + remifentanil + intubation (ETT) + Infasurf**

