Since surfactant administration procedures are already standardized in the AMC NICU, babies will have had at least one clinically indicated chest x-ray before the intervention, and a blood gas is obtained 30 to 60 minutes after the treatment, as per the routine surfactant administration protocol. The study does not alter these routine clinical protocols. Similarly, routine monitoring during the instillation of surfactant will continue, including monitoring of pulse rate, SpO_2 , colorimetric CO_2 exhalation, chest wall rise and auscultation as indicated, in all subjects.

Babies at risk for apnea of prematurity are routinely treated with caffeine. The two lower gestation age groups in this study will continue to undergo prophylactic caffeine therapy for apnea of prematurity.

Only one routine procedure will be standardized due to the study protocol. Babies with RDS on nasal CPAP all have an indwelling orogastric tube; gastric residuals are aspirated and aspirate volumes are recorded, but not always at consistent time points. For this study, the gastric residual will be suctioned before surfactant therapy in each patient, and also 15 minutes after the treatment. The amount of new gastric residual will be recorded.

Failures:

The criterion for **Early Failure** is the need for mechanical ventilation within 1 hour of surfactant therapy due to either persistent apnea, apnea despite naloxone, severe retractions, or the inability to maintain $\text{FiO}_2 < 0.60$ for target $\text{SpO}_2 90\text{-}95\%$

The criteria for **Late Failure** are one or more of the following:

- a sustained $\text{FiO}_2 > 0.60$ required to maintain target oxygen saturation,
- a second dose of surfactant within 8 hours of the first dose,
- more than 2 doses of surfactant, or
- the need for mechanical ventilation within the first 120 hours of life.

- Re-dosing of surfactant
 - Criteria for re-dosing are defined as $\text{FiO}_2 > 0.60$ or $\text{FiO}_2 > 0.30$ with associated clinical signs of worsening RDS.

- If **re-dosing surfactant before 8 hours** has elapsed from the time of initial administration, the dose will be administered via ETT for all study patients, regardless of the group to which they had been randomized.
- If **re-dosing surfactant more than 8 hours** after the initial dose, patients in the LMA group will have a second dose given via the LMA; any surfactant doses beyond the second will be given via ETT. In the ETT group, all doses are given via the ETT.

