Although the study interventions are limited to the airway used for surfactant administration in the first 1 to 3 days of life, and clinical management or follow-up are not otherwise conditioned by the study, all subjects enrolled will continue in the study up to discharge from AMC, for the purposes of data collection. This will include:

- the FiO₂ and mode of respiratory support before enrollment and at 0, 1, 12, 24, and 48 hours, and 7 and 28 days after initial surfactant administration,
- any need for additional doses of surfactant,
- any need for intubation, and
- any need for mechanical ventilation.

D. Data Analysis

A copy of the data collection sheet that will be used for the study is included.

Primary Outcome Measures: The primary outcome will be success of the surfactant administration strategy in avoiding mechanical ventilation in the first 120 hours of life.

Secondary Outcome Measures:

- Number of surfactant doses
- Days on assisted ventilation
- Day on any noninvasive respiratory support (CPAP/NIPPV modes)
- Days until off respiratory support (supplemental oxygen and/or pressure support)
- Rate pneumothorax and/or pneumomediastinum
- Rate of BPD as defined by oxygen dependence at later of 28 days or 36 weeks' postmenstrual age
- Complications during insertion of LMA or ETT
- Mortality rate

Planned post-hoc analyses include timing of failure by treatment group, which should illuminate the mechanisms of failure by treatment strategy.

➤ Baseline comparability:

Baseline differences between ETT group and LMA group will be compared using t-tests for continuous variables (birth weight, gestational age, age and FiO₂ at enrollment) and chi-square test for categorical variables (race, sex, prenatal care, antenatal steroids, mode of delivery, multiple gestation)

➤ Primary outcome measure:

Our primary outcome for the study is the proportion of infants that will reach the early and/or late failure criteria. The incidence of the failure criteria will be compared using chi-square statistics.

➤ Sample size/Power analysis:

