The sample size was estimated based on results from the recent study on this population, at the Albany Medical Center NICU. We will thus expect that 30% of the LMA group will meet failure criteria, i.e., the LMA success rate in avoiding later intubation and ventilation will be 70%. For a non-inferiority design, with a clinically relevant non-inferiority margin of 20%, a sample of 130 patients (65 per group) will be needed to conclude non-inferiority of the LMA method compared to INSURE (calculated using a one-sided $\alpha=0.05$, β error=0.20).

➤ Secondary outcome measures:

Groups will be analyzed for secondary outcome differences using chi-square statistics for categorical data, and t-test or non-parametric tests for continuous data, as appropriate for the distribution obtained. The FiO_2 response to surfactant treatment strategies will be compared from baseline to 1 and 8 hours using repeated measures ANOVA and post-hoc Dunnett's test. Time to wean off respiratory support will be compared between groups using Kaplan-Meier analysis, with censoring at discharge.

➤ Interim Analyses:

Reports for the IRB will be prepared after one year of initiation of the trial or enrollment of 50 patients, whichever comes first. Data on the primary outcome, mortality, and major adverse events on the first 50 patients, will be submitted to [name] for purposes of safety monitoring. A difference in primary outcome at the $p<0.01$ level, or a consistent trend towards differences in major adverse events will constitute criteria for recommending that the study be stopped.

E. Risks

- Risk category: Greater than minimal.

This study is considered as a greater than minimal risk study. The study design includes a decreased use of laryngoscopy for tracheal intubation, which is currently the standard method of surfactant delivery. Laryngoscopy is associated with apnea, minor abnormalities in cardiac rhythm, obstructed respiration, increase in systolic blood pressure, decreased heart rate and transcutaneous oxygen tension in preterm neonates during the laryngoscopy (Carbajal, 2007)

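### The FiO2-response analysis treats pre-treatment FiO2 as an outcome level and has no rule for readings taken after rescue, so it loses precision and could misstate an LMA oxygenation deficit in either direction.

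*Combined protocol and SAP*

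**What the plan says.** All references are to the combined protocol and SAP.

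- **Section D, Secondary outcome measures.** The FiO2 "response to surfactant treatment strategies will be compared from baseline to 1 and 8 hours using repeated measures ANOVA", followed by a post-hoc Dunnett's test. The text does not say which ANOVA term carries the between-arm comparison, what Dunnett's reference level is, or how readings after rescue are handled.
- **Section D, Baseline comparability.** FiO2 at enrollment is compared between arms by t-test. No analysis names it as a covariate.
- **Failures.** Early Failure "is the need for mechanical ventilation within 1 hour of surfactant therapy due to either persistent apnea, apnea despite naloxone", severe retractions, or failure to hold FiO2 below 0.60. Late Failure includes "a second dose of surfactant within 8 hours of the first dose".
- **Re-dosing of surfactant.** For a re-dose before 8 hours, "the dose will be administered via ETT for all study patients, regardless of the group to which they had been randomized". The trigger is itself FiO2-based: above 0.60, or above 0.30 with signs of worsening RDS.
- **Data collection list, just before section D.** The items include FiO2 "and mode of respiratory support before enrollment and at 0, 1, 12, 24, and 48 hours, and 7 and 28 days" after the first dose. Eight hours is not listed. Additional doses, intubation and ventilation are recorded.
- **Background.** The earlier single-center trial is read as showing that "surfactant delivery via LMA produces immediate improvements in oxygenation comparable to delivery via ETT".

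**The concern.** There are two separate weaknesses.

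The first is the use of baseline. FiO2 before treatment cannot be affected by the randomized route. As one level of a repeated-measures outcome, it either dilutes the treatment effect (group main effect) or turns the comparison into one of change scores (group-by-time). Used as a covariate, it would sharpen the comparison.

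The second is rescue. Infants with high FiO2 after the first dose are those selected for re-dosing or ventilation, and these tend to lower FiO2. In the LMA arm, a re-dose before 8 hours goes through the comparator's route, so the later reading no longer describes delivery by LMA alone. With no rule stated, the default is to analyze every reading as it stands.

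At stake is the plan's only between-arm analysis of FiO2 as a measurement. The Background already reads similar oxygenation in the earlier trial as evidence of comparable delivery, so a null FiO2 result could be cited in the same way. No non-inferiority margin is given for FiO2, so a non-significant ANOVA could not show comparability in any case.

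**Working it through.** **The plan's own figure.** The only sample-size figure is 130 (65 per group), for the failure rate. With 70% success in both arms (the INSURE rate is implied, not stated), a 20-point margin, one-sided alpha 0.05 and 80% power, the usual formula gives (1.645 + 0.842)² × 2 × 0.70 × 0.30 / 0.20² = 64.9, so 65 per group. It reproduces. It does not bear on FiO2, for which the documents give no mean, SD, effect size or margin. Apart from the 65 per arm, every FiO2 input below is therefore an assumption. Power is two-sided at 0.05, by normal approximation unless stated.

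**1. Baseline as an outcome level.** Assume SD 0.10 at each time, a common correlation r between times, and a true LMA deficit of 0.05 at both 1 and 8 hours.

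- Group main effect over three levels: (0 + 0.05 + 0.05)/3 = 0.033, a loss of one-third.
- Group-by-time contrast (mean of the two post-treatment values minus baseline): expected value 0.05, unbiased.
- ANCOVA on the mean of the two post-treatment values: expected value 0.05.

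| r | Main effect | Group-by-time | ANCOVA |
|---|---|---|---|
| 0.3 | 74% | 79% | 97% |
| 0.5 | 64% | 91% | 98% |
| 0.7 | 57% | 99% | 99.7% |

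At a single follow-up time, the variance ratio of ANCOVA to change score is (1 − r²)/(2(1 − r)) = (1 + r)/2. This is 0.60 at r = 0.2 and 0.80 at r = 0.6.

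**2. Readings after rescue: a worked example.** Assume 75% of LMA and 95% of INSURE infants respond. FiO2 is 0.25 in responders and 0.60 in non-responders before rescue. Every non-responder is rescued, to 0.30 or 0.40.

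- Pre-rescue means: 0.75 × 0.25 + 0.25 × 0.60 = 0.3375 and 0.95 × 0.25 + 0.05 × 0.60 = 0.2675. Difference 0.07.
- Post-rescue at 0.30: 0.2625 and 0.2525. Difference 0.01.
- Post-rescue at 0.40: 0.2875 and 0.2575. Difference 0.03.

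The SD must include the spread between responders and non-responders: variance = within-group SD² + p(1 − p) × (gap)². At within-group SD 0.10:

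- Pre-rescue: SDs 0.182 and 0.126, SE √((0.182² + 0.126²)/65) = 0.0274, power about 72%.
- Post-rescue 0.30: SE 0.0178, power about 9%.
- Post-rescue 0.40: SE 0.0197, power about 33%.

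At within-group SD 0.05, the figures are about 87% pre-rescue against 19% and 66%. Pre-rescue power cannot exceed about 91% on these inputs, because the mixture alone gives SDs of 0.152 and 0.076.

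**3. Does the direction hold?** A simulation (1,500 runs per scenario) assumed SD 0.10, r = 0.5, mean FiO2 0.40 at baseline and 0.30 after INSURE, and a floor at 0.21. Infants with the highest 1-hour FiO2 were rescued, which lowered their 8-hour FiO2 by 0.10 or 0.20. Power is for the 8-hour change-score test.

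| True deficit | Rescued LMA / INSURE | 8-hour difference seen | Power |
|---|---|---|---|
| 0.05 | none | 0.043–0.044 | 74–75% |
| 0.05 | 20% / 10% | 0.024–0.033 | 21–45% |
| 0.05 | 30% / 10% | 0.008–0.023 | 3–24% |
| 0.05 | 30% / 30% | 0.035–0.041 | 35–60% |
| 0.05 | 10% / 30% | 0.060–0.069 | 95–96% |
| 0.10 | 30% / 10% | 0.049–0.070 | 69–98% |

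The distortion shrinks the deficit when rescue is commoner with LMA and enlarges it when rescue is commoner with INSURE. In this model the 1-hour reading precedes rescue, and its power for a 0.05 deficit stays at 71% to 78%.

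**The case against.** A reader might infer that the planned analysis would show comparable oxygenation even if the LMA delivered less surfactant. The documents do not support that, for five reasons.

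- **Direction.** It requires more rescue in the LMA arm. The earlier trial described in the Background had fewer failures with LMA, and the INSURE failures were linked to morphine. Remifentanil may change this, but the sign of the distortion is unknown. The protocol also states that "Criteria for assisted ventilation and other respiratory support will be the same for both groups".
- **Timing.** The Background claim concerns immediate improvement. The nearest reading here is at 1 hour, which is affected mainly by early failures.
- **Primary outcome.** Ventilation and re-dosing within 8 hours count as failure. In the worked example, failure would be 25% against 5%, and the planned chi-square test would detect that about 92% of the time. A non-inferiority test at the 20-point margin would pass only about 6% of the time. Poor delivery on that scale would not go unseen.
- **Estimand.** The text compares treatment strategies, and a comparison with rescue included is a legitimate question.
- **Baseline.** If group-by-time is tested, baseline as a level biases nothing.

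All five points stand against the stronger reading. They do not supply the missing rule, name the tested term, or recover the precision lost by not adjusting. A treatment-policy reading is defensible only if it is declared, because it does not answer whether delivery by LMA was as good.

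**Conclusion.** The concern holds in limited form. Using baseline FiO2 as an ANOVA level costs one-third of the effect if the main effect is reported. Otherwise it costs precision, with ANCOVA variance 60% to 80% of the change-score variance for correlations of 0.2 to 0.6. Separately, with no rule for post-rescue readings, the later comparison could understate an LMA deficit, or overstate it if rescue is commoner with INSURE. In the assumed example, power is about 9% to 33% against about 72% with pre-rescue values, at within-group SD 0.10. A large deficit (0.10) stays detectable in most of the simulated scenarios.

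The sizes rest on assumed FiO2 means, SDs, correlations and rescue shares. The structural points rest on the text alone: the handling of baseline, the silence on rescue, and the 8-hour time missing from the collection list. This is one secondary analysis, not in the section D list of secondary outcomes, and it leaves the primary conclusion unchanged.

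**What to change.** 1. Replace the repeated-measures ANOVA and Dunnett's test with a between-arm FiO2 difference and confidence interval at each time, with enrollment FiO2 as covariate (ANCOVA, or a mixed model with a common baseline).
2. State whether the main FiO2 comparison includes readings after rescue. Report by arm the number of infants ventilated or re-dosed before each reading.
3. Add a sensitivity analysis that does not take post-rescue FiO2 at face value, such as the last available pre-rescue value or a worst rank. Worst rank also penalizes infants ventilated for apnea after full surfactant delivery, which may fall more on INSURE. It gives a rank comparison rather than a mean difference, so show it beside the main result.
4. Reconcile the 8-hour analysis time with the collection list, either by adding an 8-hour FiO2 or by moving the analysis to a listed time.

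Items 1 and 2 need only SAP wording, since enrollment FiO2, mode of support, extra doses, intubation and ventilation are already recorded; the counts also need the times of these events. Items 3 and 4 may need an extra entry on the data sheet: neither an 8-hour nor a last pre-rescue FiO2 is in the listed schedule, and the sheet itself could not be seen.

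### The plan schedules one by-arm safety review with stopping criteria, at 50 patients or one year; 80 of the 130 infants enrol after it with no further scheduled by-arm comparison

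*Combined protocol and SAP*

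**What the plan says.** All references are to the combined protocol and SAP.

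- **Timing** (D. Data Analysis, Interim Analyses): "Reports for the IRB will be prepared after one year of initiation of the trial or enrollment of 50 patients, whichever comes first".
- **Content** (same paragraph): "Data on the primary outcome, mortality, and major adverse events on the first 50 patients" go to a named recipient, masked in the public copy, for safety monitoring.
- **Stopping criteria** (same paragraph): a primary-outcome difference at p<0.01, in either direction, or "a consistent trend towards differences in major adverse events will constitute criteria for recommending that the study be stopped".
- **Size and duration**: "a sample of 130 patients (65 per group) will be needed to conclude non-inferiority of the LMA method compared to INSURE" (Sample size/Power analysis), and "It is anticipated that the study will take 2 years to complete" (B. Study Design/C. Subject Population).
- **Risk class** (E. Risks): greater than minimal.
- **Other safety reporting** (E. Risks, adverse event subsections): investigators monitor each subject throughout. Adverse events not explained by the underlying illness go to the IRB and are followed up. Every serious adverse event goes to the IRB within 24 hours. Serious events possibly related to the device also go to the manufacturer and the FDA. No comparison between arms and no stopping criterion is attached to these reports.

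No second interim report or later by-arm review appears anywhere in the document.

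**The concern.** Single-case reports and by-arm tables answer different questions. Air leak, pulmonary hemorrhage, chronic lung disease and death are all listed in E. Risks as expected in this population. One more case is unremarkable when read alone; an excess in one arm shows only when cases are counted by arm against a denominator. The plan schedules that count once, early, when few events have occurred. An imbalance that emerges or becomes readable later has no scheduled occasion on which it would be seen and no criterion under which stopping would be recommended.

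The timing rule also has a gap. It takes the earlier of two triggers, but the content is defined by only one of them, the first 50 patients. Slow accrual is not far-fetched: the background section records that a comparable trial of surfactant by LMA stopped early because of it.

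**Working it through.** **Inputs.** From the plan: 130 infants, 65 per arm; 2 years; review at 50 patients or one year; p<0.01 for the primary outcome; mortality 1% to 5% (expected adverse events table); LMA failure 30% ("We will thus expect that 30% of the LMA group will meet failure criteria"); margin 20 points; one-sided alpha 0.05; power 0.80. Assumptions: INSURE failure is also 30%, since the plan gives no figure; accrual is even; arms are equal in size at each look.

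**Step 1. The plan's sample size.** n per arm = (1.645 + 0.842)² × (0.70×0.30 + 0.70×0.30) / 0.20² = 64.9, rounded up to 65, total 130. This matches the plan.

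**Step 2. When the review falls.** 130/24 = 5.42 infants per month, so the 50th enrols at 50/5.42 = 9.2 months. Infants enrolled afterwards: 130 − 50 = 80, and 80/130 = 61.5%. About 24 − 9.2 = 14.8 months of enrolment follow.

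**Step 3. When one year comes first.** This needs fewer than 50 infants per year, that is, 130 infants taking more than (130/50) × 12 = 31.2 months.

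| Time to enrol 130 | Enrolled at review | Enrolled after |
|---|---|---|
| 24 months (plan) | 50 | 80 |
| 36 months | about 43 | about 87 |
| 48 months | 32–33 | 97–98 |
| 60 months | 26 | 104 |

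**Step 4. Deaths available to the review.** Expected: 50 × 0.01 = 0.5 to 50 × 0.05 = 2.5. Chance of none: 0.99^50 = 61% and 0.95^50 = 8%.

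**Step 5. Primary outcome, one look against two.** The test is the chi-square at two-sided p<0.01, counted only when LMA is worse, on cumulative data at 25 and then 50 per arm. Probabilities come from binomial enumeration.

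| True failure, LMA vs INSURE | Flagged by one look | Flagged by either of two |
|---|---|---|
| 50% vs 30% (difference equal to the margin) | 13% | 33% |
| 30% vs 30% (false flag) | 0.5% | 0.9% |

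**Step 6. Effect on the final test.** With 30% failure in both arms, a Wald upper bound at one-sided 5% and looks that stop only against LMA, non-inferiority power is 80.6% with one look and 80.6% with two. Stopping when LMA looks worse only removes trials that might have claimed non-inferiority, so it cannot raise the type I error.

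**Step 7. If the criterion stayed two-directional.** With equal arms at 30%, the false-stop probability is 1.0% for the single look. It is 2.1% for looks at 50 patients, month 12 (about 65 patients) and 100 patients.

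**The case against.** **Infants after the 50th are not unmonitored.** A reader might infer that safety review ends at the interim report. The documents do not support that: subject-level monitoring, 24-hour serious event reports and follow-up run for every infant. What is absent is narrower, namely a scheduled by-arm comparison with a stopping criterion.

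**The shortfall below 50 is conditional.** At the planned pace about 65 infants enrol in year one and the conflict does not arise. The paragraph can also be read as two submissions, an IRB report at the earlier trigger and a separate safety submission once 50 are in. That reading is possible but not stated, so a clarification is still needed.

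**The adverse-event criterion is not unworkable at one look.** A reader might infer that a consistent trend needs repeated looks. Consistency could equally mean agreement across event types, centres or gestational-age strata, so this is not part of the point.

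**The p<0.01 level does not govern adverse events.** The plan applies it to the primary outcome only. The detection rates above therefore say nothing about pneumothorax or other events, for which no numerical rule exists.

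**The benefit is limited.** A look at 100 directly protects only about the last 30 infants, and two looks still miss about 67% of trials with the modelled harm. This stands, and it argues for modest expectations of the added look.

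**The recipient is masked.** Nothing can be concluded about whether a monitoring body exists, and this point makes no such claim.

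**Conclusion.** The point holds in this form: one scheduled by-arm review with stopping criteria, at about month 9 on the planned pace, with 80 of 130 infants (62%) enrolling after it and only case-level reporting thereafter. If accrual falls below 50 per year, more than 80 infants follow the review and its content is not clearly defined. The single look would see 0.5 to 2.5 deaths in total. It would flag a failure difference as large as the plan's own margin in 13% of trials, against 33% with a second cumulative look.

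The review date rests on even accrual over 2 years, and the flag rates on 30% failure with INSURE and equal arms at each look. The count of 80 needs only that 50 infants are reached within the first year. This is a gap in the monitoring schedule that should be closed in a greater-than-minimal-risk trial; it does not undermine the primary analysis.

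**What to change.** In the Interim Analyses paragraph:

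1. Make the reports cumulative on all infants enrolled to date, due at 50 and again at 100 patients, and also at one year if 50 has not been reached by then.
2. Use the same by-arm table (primary outcome, mortality, major adverse events) and the same recipient each time.
3. State that at the added report the primary-outcome criterion is used only for a difference unfavourable to LMA. Adverse-event review continues under the sponsor's existing criterion.

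**Cost.** Protocol wording and one or two more runs of a table already planned. With equal arms at 30%, the false harm flag on the primary outcome rises from about 0.5% to 0.9%. It would reach about 2.1% if the either-direction criterion and a month-12 look were used instead, which is why item 3 matters. Repeating the adverse-event trend criterion adds some further chance of a false alarm; it cannot be computed because that criterion has no number attached. Power stays at about 80.6% and the non-inferiority type I error does not rise.
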